13. DATA ANALYSIS AND MANAGEMENT *

Hypothesis: Prophylactic tamsulosin decreases the rate of postoperative urinary retention (POUR) rates in patients undergoing thoracic surgery

- Primary aim: compare the rates of POUR in thoracic surgery patients treated with preop tamsulosin with historic controls.

INVESTIGATOR STUDY PLAN

The rates of POUR for major procedures in UMass Thoracic service in the target population (male over 60 years old) varied from 8.3% to 33.3% over the last 5 years. In the overall thoracic population, this number was in average 8.4% and it varied from 4.3% to 9.3%.

When analyzing all major procedures performed in the 2019, 48 were performed in males over 60 years old, the study target population. The POUR rate was 33.3%. After applying the exclusion criteria on those 48 individuals, we found an exclusion rate of 33.3% where 16 individuals were excluded, 8 for using Flomax prior to surgery and 8 for using one of the following medications: Bupropion Fluconazole, TMP-SMX, Silodosin, Paroxetine Terazosin, Levofloxacin, Prazosin, Fluoxetine, Sildenafil.

The overall POUR rate was 33% and among the 32 eligible individuals, POUR rate was 28%.

Power Calculation

The incidence rate of 28% was used to estimate the possible scenarios of sample and power of analysis presented in **Error! Reference source not found.**

The number needed to treat is 60 assuming an 80% reduction of POUR with a power of 80%. Assuming the same volume of operations and taking into account the number excluded due to exclusion criteria (33%), and refusal rate of 25%, we expect to accrue 24 patients per year and achieve the number needed to treat (n=60) in 2.5 years.

All patients who fulfill the eligibility criteria and thus may benefit from the intervention (use of Tamsulosin pre-operatively) will be invited to participate in the study. **(Error! Reference source not found.)**

Table 1. Sample calculation and power-analysis in three hypothetical scenarios of varying effects of tamsulosin

	Hypothetical POUR Incidence in Intervention Group (%)	N*	Post-hoc Power estimate (I)
Tamsulosin intervention Group effect 1 (reduction of 50%)	14	150	49.3%
Tamsulosin intervention Group effect 2 (reduction of 80%)	5.6	60	80.4%
Tamsulosin intervention Group effect 3 (reduction of 90%)	2.8	32	80.4%

*N of male over 60 years old that undergo to in-patient procedures (I) <https://clincalc.com/stats/SampleSize.aspx>

INVESTIGATOR STUDY PLAN

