(II) <https://jongguri.shinyapps.io/samplepower/>

The study selected parameters are:

- Incidence, group historical control 2019 – 28%
- Incidence (expected), intervention with Tamsulosin – 5.6% (reduction of 80% in incidence)
- Subjects, group control – 32 individuals
- Subjects, group intervention (expected) -60 individuals
- Alpha - 0.05

It is expected that the population undergoing thoracic services are similar over time and it will be appropriate to use historical controls to compare with the intervention group.

Our analytical plan is to test the proportion of POUR within the study population comparing with the historical controls. The data quality will be monitored by monthly verification of the completeness of the data, missing values and accurateness of the variables collected.

If a statistically significant reduction in POUR rates is observed before the end of the study, the study will stop and Tamsulosin will be adopted as prophylaxis for this high-risk population in thoracic surgery division. If the benefit is not observed with the estimated sample, the study will be reassessed.

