14. PROVISIONS TO MONITOR THE DATA TO ENSURE THE SAFETY OF SUBJECTS*

We will analyze the patients' outcomes every 2 months and monitor them for possible side effects associated with tamsulosin: hypotension, insomnia, decreased libido, nausea, diarrhea and dizziness.

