21. SHARING OF RESEARCH RESULTS WITH SUBJECTS*

The dissemination of the research results will be performed through interim reports, presentations for the UMass Memorial Health Care and UMass Medical School health professionals. Scientific abstracts and papers will focus on sharing the results with the scientific community. As a very relevant topic, it is intended to disseminate the results beyond the scientific community, with the appropriate materials and language (flyers and fact sheets) to the policy makers, health care professionals and overall population, including the subjects that took part in the study. Individual results will be shared with the subjects if requested.

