23. RESOURCES AVAILABLE

In this study, we assemble the following research team: three thoracic surgeons, one of them being the principal investigator (PI); statistician and six research assistants from UMass Medical - medical students, residents, fellows or other healthcare providers pool. The roles will be as follows:

Principal Investigator/thoracic surgeon: Recruit subjects, perform minimally invasive thoracic surgery, and prescribe tamsulosin according to procedures described in section #11. She will also help analyze the data. Five percent of the PI's time will be dedicated to the project. The PI is a fellowship trained thoracic surgeon with a Master's degree in Biostatistics and Patient Oriented Research. She has published many studies focused on surgical patient-oriented outcomes.

Thoracic surgeons (2 other thoracic surgeons in the division of Thoracic Surgery): Recruit subjects. Perform minimally invasive thoracic surgery and prescribe tamsulosin according to procedures described in section #11. Provide preop and post-operative care for patients.

Research assistants: describe the study and consent subjects. Query subjects on potential adverse effects of tamsulosin. Perform data collection that will be supervised by the PI and statistician. They will have CITI training and be a trained University of Massachusetts health care provider, such as nurse, medical student, resident, or fellow.

Statistician and research coordinator: Analyze the data monthly for quality purposes and at the time of study conclusion. Assist in research protocol development and oversee data collection.

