25. LOCAL NUMBER OF SUBJECTS

Considering the volume of procedures in 2019 of 48 procedures is maintained over time, it is estimated that we will be able to enroll 60 patients within 2.5 years. This sample size would allow detection of 80% reduction in POUR with a power of 80%. This number of subjects considers a refusal rate of 25% and exclusion rate of 33%.

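### Section 13 stops the study and adopts tamsulosin at any significant result before the end, with one alpha of 0.05 and no stated looks, minimum sample or boundary

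*Combined protocol and SAP*

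**What the plan says.** Section 13 sets the operative rule: "If a statistically significant reduction in POUR rates is observed before the end of the study, the study will stop", and tamsulosin is then adopted for this population in the division. The analysis is described as follows: "Our analytical plan is to test the proportion of POUR within the study population comparing with the historical controls". No test is named and sidedness is not given. The parameter list has a single alpha of 0.05, 32 controls at 28%, and 60 treated patients expected at 5.6%.

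The sample size is for one comparison at the full sample. Section 13 expects to "achieve the number needed to treat (n=60) in 2.5 years", and section 25 repeats the claim: "This sample size would allow detection of 80% reduction in POUR with a power of 80" percent. If the result is negative, section 13 adds: "If the benefit is not observed with the estimated sample, the study will be reassessed".

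Four other statements bear on when data are examined:
- Section 14, under safety, has the team analyse "outcomes every 2 months and monitor them for possible side effects".
- Section 13 has a monthly check of completeness and accuracy.
- Section 23 has the statistician and coordinator "Analyze the data monthly for quality purposes and at the time of study conclusion".
- Section 21 says "dissemination of the research results will be performed through interim reports", without timing or content.

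**The concern.** The rule allows the same 0.05 test to be applied to accumulating data at any time and any number of times, and the first significant result ends the study and changes practice. A threshold of 0.05 controls the error of one test, not of the first success in an unspecified series.

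The other sections do not close the gap. Section 23 provides for no efficacy analysis before the study concludes, yet section 13 needs one for its rule to operate. The two-monthly and monthly reviews are for safety and quality, but each is an occasion on which the rule could be triggered. The statement on reassessment also does not say whether more patients could be enrolled and the test repeated.

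Two things are at stake: the error rate of a decision that changes practice, and the credibility of the estimate. With no minimum sample, a stop can come when very few patients have been treated, at a point selected because the observed rate is low.

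**Working it through.** **Inputs from section 13.** Controls 32 at 28% (28% of 32 is 8.96, so 9/32); treated 60 at 5.6%; alpha 0.05; accrual 24 per year.

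**Assumptions, because the plan does not state them.** Two-sided 0.05, with only the benefit direction counted (nominal 2.5%); Fisher's exact test or the pooled chi-square without continuity correction; several possible look schedules.

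**1. The plan's power.** Pooled-variance normal approximation, one test:
- pooled rate = (8.96 + 3.36)/92 = 0.1339
- SE under no difference = √[0.1339 × 0.8661 × (1/32 + 1/60)] = 0.0745
- SE under the design = √[0.28 × 0.72/32 + 0.056 × 0.944/60] = 0.0847
- power = Φ[(0.224 − 1.96 × 0.0745)/0.0847] = Φ(0.919) = 82.1%

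Table 1 states 80.4%. The same formula gives 49.3% for the 14% row (stated 49.3%) and 81.3% for the 2.8% row (stated 80.4%). Exact power for the n=60 row is 80.5% (Fisher) or 85.0% (chi-square). The stated powers therefore fit a single two-sided test and make no allowance for early looks.

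**2. Chance of a false benefit.** Exact binomial recursion over the looks, true rate 28% in both groups, stopping at the first two-sided p < 0.05 with the treated rate lower. Two-monthly looks mean 24/6 = 4 patients per look and 60/4 = 15 looks. Each cell is Fisher / chi-square.

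| Schedule | Controls drawn from Bin(32, 0.28) | Controls fixed at 9/32 |
|---|---|---|
| n=60 only | 2.1% / 2.6% | 0.065% / 0.21% |
| n=30 and 60 | 2.9% / 3.8% | 0.45% / 0.56% |
| 15 two-monthly looks | 5.5% / 7.4% | 2.6% / 3.2% |
| after every patient | 6.8% / 9.5% | 2.7% / 4.4% |

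If 0.05 were one-sided, the normal test with random controls gives 5.2% for one look and 14.7% for 15.

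**3. Earliest possible stop against 9/32.** 0/11 gives chi-square p = 0.048; 0/12 gives Fisher p = 0.047. At 24 patients per year, 12 patients is 12/24 = 0.5 year. The exact 95% upper limits for the treated rate are 1 − 0.025^(1/11) = 28.5% and 1 − 0.025^(1/12) = 26.5%, against a control rate of 28%.

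**4. Overstatement.** Mean observed treated rate among trials that reach significance (random controls; ranges span the two tests):

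| True treated rate | One test at n=60 | n=30 and 60 | 15 looks |
|---|---|---|---|
| 5.6% | 5.0% to 5.1% | 4.4% to 4.6% | 3.2% to 3.3% |
| 14% (chi-square) | 11.3% | not shown | 7.2% |

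With 15 looks and a true 5.6%, the mean stopping point is 21 to 23 patients. At a true 14% (the 50% reduction in Table 1), a mean of 7.2% set against 28% reads as a reduction of 1 − 7.2/28 = 74%; the single test's 11.3% reads as 60%.

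**The case against.** The core of the point is not disputed, but its size is. The larger error figures need 15 or more efficacy looks, which no section schedules; the two-monthly review belongs to safety. With one unadjusted interim the error is 2.9% or 3.8%. With controls held at 9/32, 15 looks give 2.6% or 3.2%, close to nominal. Overstatement is an average over trials, and at the assumed 5.6% it is about 2.4 points on a planned difference of 22.4. Stops at 0/11 are rare under no effect (0.72^11 = 2.7%). The reassessment sentence mentions no retest.

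All of this limits the magnitude and stands as a limit. It does not supply the missing rule: error rises with the number of looks in every version, and the plan sets no upper bound on that number. The reassessment sentence needs only clarification and is not evidence of inflation.

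A further objection is that a single test does not secure the error rate either, because the control rate may drift. Section 13 reports 8.3% to 33.3% over five years in the target population. If the untreated rate during the study were 15% (an assumption inside that range), an ineffective drug would pass one test against 9/32 in 18% (Fisher) or 30% (chi-square) of trials. That is correct, but it is a separate weakness of the historical comparison. Fixing the looks does not cure it and should not be presented as doing so.

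**Conclusion.** The concern holds. As written, the stop-and-adopt decision has no determinable error rate, and the single alpha of 0.05 does not describe it. Under the two-sided assumption with random controls, the chance of a false benefit runs from 2.1% to 2.6% (one test) up to 6.8% to 9.5% (a look after every patient), with 5.5% to 7.4% for two-monthly looks. It is lower with controls fixed at 9/32, but still rises from at most 0.21% to as much as 4.4%. The average overstatement is modest at the assumed 80% reduction and substantial at a 50% reduction. All figures rest on an assumed test, sidedness, schedule and treatment of the controls, none of which the plan states. Because the rule governs the primary conclusion and a change of practice, it must be settled before POUR rates are compared with the controls.

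**What to change.** Replace the open rule in section 13 with one efficacy test, by a named method at two-sided 0.05, when the 60th treated patient has a POUR outcome, and tie the adoption statement to that test. State that the two-monthly and monthly reviews cover safety and data quality only and do not compare POUR rates with the controls. State that reassessment does not include further enrolment and retesting at an unadjusted 0.05. Bring sections 13, 14, 21 and 23 into agreement on when efficacy is tested.

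This is three or four sentences. Exact power stays at 80.5% (Fisher) or 85.0% (chi-square). What is lost is the option to stop at any review.

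If an early look is wanted, pre-specify one at n=30. Because all 32 controls are available from the start, the information fraction is (1/32 + 1/60)/(1/32 + 1/30) = 0.742, not 0.5. O'Brien-Fleming-type spending of one-sided 0.025 then gives two-sided thresholds of about 0.0185 at the interim and 0.044 at the end. Results, Fisher / chi-square: power 77.2% / 84.8%, benefit-direction error 2.1% / 2.9%, chance of an early stop under the design effect 42% / 53%. The 2.9% exceeds 2.5%, so the boundary should be checked exactly for the test chosen.

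A stricter fixed pair of 0.003 and 0.049 (not the O'Brien-Fleming boundary for this design) keeps power at 80.5% / 85.0% and error at 2.1% / 2.6%, but stops early only about 21% of the time.

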14. PROVISIONS TO MONITOR THE DATA TO ENSURE THE SAFETY OF SUBJECTS*

We will analyze the patients' outcomes every 2 months and monitor them for possible side effects associated with tamsulosin: hypotension, insomnia, decreased libido, nausea, diarrhea and dizziness.

15. WITHDRAWAL OF SUBJECTS WITHOUT THEIR CONSENT*

NA

16. RISKS TO SUBJECTS*

INVESTIGATOR STUDY PLAN

The primary risks to the participants include the side effects associated with tamsulosin: hypotension, insomnia, decreased libido, nausea, diarrhea and dizziness.

17. POTENTIAL DIRECT BENEFITS TO SUBJECTS*

The primary direct benefit to the participants includes decreased urinary retention post-operatively, which is one of the most common and uncomfortable complications many patients face. Decreased urinary retention will also decrease the need for potential re-catheterization. It is difficult to accurately predict the probability of this benefit because results vary depending on the type of surgery and pre-operative risks; however, several studies have documented the successes of prophylactic tamsulosin. ^{1,12-14}

18. VULNERABLE POPULATIONS*

NA

19. MULTI-SITE RESEARCH*

NA

20. COMMUNITY-BASED PARTICIPATORY RESEARCH*

NA

21. SHARING OF RESEARCH RESULTS WITH SUBJECTS*

The dissemination of the research results will be performed through interim reports, presentations for the UMass Memorial Health Care and UMass Medical School health professionals. Scientific abstracts and papers will focus on sharing the results with the scientific community. As a very relevant topic, it is intended to disseminate the results beyond the scientific community, with the appropriate materials and language (flyers and fact sheets) to the policy makers, health care professionals and overall population, including the subjects that took part in the study. Individual results will be shared with the subjects if requested.

22. SETTING

INVESTIGATOR STUDY PLAN

The research will solely take place at UMMHC Memorial Campus.

23. RESOURCES AVAILABLE

In this study, we assemble the following research team: three thoracic surgeons, one of them being the principal investigator (PI); statistician and six research assistants from UMass Medical - medical students, residents, fellows or other healthcare providers pool. The roles will be as follows:

Principal Investigator/thoracic surgeon: Recruit subjects, perform minimally invasive thoracic surgery, and prescribe tamsulosin according to procedures described in section #11. She will also help analyze the data. Five percent of the PI's time will be dedicated to the project. The PI is a fellowship trained thoracic surgeon with a Master's degree in Biostatistics and Patient Oriented Research. She has published many studies focused on surgical patient-oriented outcomes.

Thoracic surgeons (2 other thoracic surgeons in the division of Thoracic Surgery): Recruit subjects. Perform minimally invasive thoracic surgery and prescribe tamsulosin according to procedures described in section #11. Provide preop and post-operative care for patients.

Research assistants: describe the study and consent subjects. Query subjects on potential adverse effects of tamsulosin. Perform data collection that will be supervised by the PI and statistician. They will have CITI training and be a trained University of Massachusetts health care provider, such as nurse, medical student, resident, or fellow.

Statistician and research coordinator: Analyze the data monthly for quality purposes and at the time of study conclusion. Assist in research protocol development and oversee data collection.

24. LOCAL RECRUITMENT METHODS

Potential subjects will be identified and recruited when they visit the clinic, and the thoracic surgeons will ask them permission for the study staff to approach. Each clinician on the study team will only invite their own patients to participate in the study. In addition, inpatients who require the appropriate surgeries will also be identified by thoracic surgeons.

INVESTIGATOR STUDY PLAN

Individuals who are eligible for the research study will be adult men >60 years old who need to undergo some type of thoracic surgery procedure (See #6 for more detailed inclusion criteria). The patients' names and MRN will be recorded electronically, and the patients' names will be replaced by a code. The identifiers will be destroyed after 6 years after the study completion. Identifiers will not be recorded for patients who are ineligible or those who decline to participate.

Recruitment will be done during clinic visit or in UMass Memorial Hospital. Advertisements and other recruitment materials including flyers, emails, and letters will not be utilized. There will be no payments to the subjects.

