The age cutoff is debatable, but in general, it is accepted that older age correlates with numerous types of bladder dysfunction ⁶. There are also certain procedures within thoracic surgery that increase the risk. Lung resection surgery resulted in the highest rate of POUR compared to other procedures like sympatheticotomies, pleural biopsies, and mediastinal procedures ¹. In a review of all UMass Memorial patients who underwent thoracic surgery in 2019, the group with the highest incidence of POUR consisted of males above the age of 60 who underwent major thoracic resections. The rate in this cohort was as high as 21%. Although tamsulosin was designed and used to treat patients with symptomatic BPH, we would like to study the effect of prophylactic tamsulosin in the group of patients with the highest likelihood to develop POUR in an effort to prevent this complication.

Post-operative urinary retention is a prevalent complication. Patients who undergo thoracic surgery have greater urinary retention rates compared to others. Data on effective methods to reduce the risk of POUR in this high-risk group are limited.

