6. INCLUSION AND EXCLUSION CRITERIA*

Inclusion criteria:

- All male patients ≥ 60 years old undergoing inpatient thoracic surgery for major resections.

Exclusion criteria:

- Prisoners
- Adults unable to consent
- End stage renal disease on hemodialysis
- Indwelling urinary catheter
- Child-Pugh class C hepatic failure
- Usage of the following medications prior to surgery: strong CYP 3A4 inhibitors, other alpha-adrenergic blocking agents.

INVESTIGATOR STUDY PLAN

- patients known to be CYP2D6 poor metabolizers
- History of prostatectomy or cystectomy
- Patients with contraindications to tamsulosin and those at high risk for side effects: hypersensitivity to tamsulosin HCl or any component of FLOMAX capsules,⁵ hypersensitivity to sulfonamides. History of known glaucoma, hypotension, plan to undergo cataract surgery in the next 2 weeks

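### The 28% control rate is not shown to come from the population that Section 6 enrols, and the planned test makes no allowance for operation type

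*Combined protocol and SAP*

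**What the plan says.** The treated group is set by Section 6: "All male patients ≥ 60 years old undergoing inpatient thoracic surgery for major resections".

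The controls are set in Section 13: "When analyzing all major procedures performed in the 2019, 48 were performed in males over 60 years old, the study target population". The study exclusions then remove 16 of the 48. The remaining 32 have a POUR rate of 28%, and these two figures go into the power calculation.

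Two other places describe the population more loosely. The Table 1 footnote counts men over 60 having in-patient procedures, without the word major. Section 24 speaks of "adult men >60 years old who need to undergo some type of thoracic surgery procedure", but the same sentence points back to the eligibility list: "some type of thoracic surgery procedure (See #6 for more detailed inclusion criteria".

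Section 5 reports a separate look at the same year: "In a review of all UMass Memorial patients who underwent thoracic surgery in 2019", the group with the highest incidence was men above 60 having major thoracic resections, at up to 21%. Section 5 also says that operation type matters: "Lung resection surgery resulted in the highest rate of POUR compared to other procedures".

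On analysis, Section 13 plans a test of the POUR proportion against the historical controls and expects the thoracic population to be similar over time. Section 11 lists type of surgery among the data to be collected, but no section uses it for adjustment or stratification. Section 27 mentions matching once and names no variables.

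**The concern.** The comparison with 2019 controls is the trial's only test of the drug. It is interpretable only if both groups are drawn by the same rule. Here one group is selected on resections and the other on procedures, neither term is defined or listed, and the plan itself says that risk depends on the operation. A difference in case mix would move the POUR difference with no drug effect, and an unadjusted test of proportions would not remove it.

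The two 2019 rates make this more than a question of style. They concern the same year, the same sex, the same over-60 wording and apparently the same service, yet they are far apart. The stakes are high because Section 13 says that a significant reduction ends the study and leads the division to adopt tamsulosin prophylaxis.

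**Working it through.** **1. The plan's counts.** 33.3% of 48 is 16 men with POUR. Exclusions are 16/48 = 33.3%, leaving 32. A rate of 28% in 32 men is 9/32 = 28.1%. Accrual is 48 × (1 − 1/3) × (1 − 0.25) = 24 a year, and 60/24 = 2.5 years. These figures all descend from the Section 13 wording.

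**2. The plan's power.** Inputs from Section 13: p1 = 0.28, n1 = 32; p2 = 0.056, n2 = 60; alpha 0.05. Sidedness is not stated; two-sided fits Table 1 and one-sided (88.4%) does not.
- Pooled proportion = (8.96 + 3.36)/92 = 0.1339.
- SE under no difference = √[0.1339 × 0.8661 × (1/32 + 1/60)] = 0.0745.
- SE under the alternative = √[0.28 × 0.72/32 + 0.056 × 0.944/60] = 0.0847.
- Power = Φ[(0.224 − 1.96 × 0.0745)/0.0847] = Φ(0.92) = 82.1%.

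Exact enumeration with Fisher's test gives 80.5%. The plan states 80.4%, so its figure is reproduced.

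**3. The definitions side by side.**

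| Place | Age | Operation |
|---|---|---|
| Section 6 (treated) | 60 or over | inpatient, major resections |
| Section 13 (controls) | over 60 | major procedures |
| Table 1 footnote | over 60 | in-patient procedures |
| Section 24 | over 60 | any thoracic procedure, deferring to Section 6 |
| Section 5 (21% rate) | above 60 | major thoracic resections |

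**4. The two 2019 rates.** The gap is 33.3 − 21 = 12.3 points before exclusions and 28 − 21 = 7 points after them. Suppose resections were a subset of the 48 with a 21% rate. The other operations would then need a rate above 33.3% for the whole to average 33.3%. That sits badly with Section 5, which calls the 21% cohort the highest-incidence group. A different case set, a different way of counting POUR, or an error could each be the cause, and the documents do not say which.

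**5. Illustration of the effect on error.** Assume no drug effect, 32 controls with true rate 28%, 60 treated men with true rate 21%, and a two-sided 0.05 test. Count only significant results favouring tamsulosin.
- Normal approximation: pooled proportion = (8.96 + 12.6)/92 = 0.2343; null SE = 0.0927; alternative SE = √[0.2016/32 + 0.1659/60] = 0.0952. Chance = Φ[(0.07 − 1.96 × 0.0927)/0.0952] = Φ(−1.17) = 12.0%.
- Exact enumeration over both binomials: 12.1% (chi-square), 9.9% (Fisher).
- Same enumeration with 28% on both sides: 2.6% and 2.1%.

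These figures treat the control count as random. If it is held at the observed 9/32, significance needs at most 7 treated events (chi-square) or 6 (Fisher). The chance is then 4.6% or 2.0% at a treated rate of 21%, against 0.2% or 0.06% at 28%. The level is lower, but the relative rise is larger.

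**6. Effect on power.** If a repeated query gave 21%, with the same 80% reduction (to 4.2%) and the same 32 and 60, the formula in step 2 gives 69.5% instead of 82.1%.

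**The case against.** The best defence is that the plan intends one population. Section 13 calls the 48 the target population, applies the study exclusions to them and calls the 32 eligible. Both sides are restricted to major operations in older men, and nothing in the documents shows a major non-resection among the 48. The two rates need not reflect different operations either: 10/48 = 20.8%, which rounds to 21%, so the same 48 men with a different event count would also produce the Section 5 figure. This stands as far as it goes. A different case set is not proved, but the documents do not rule it out, and a different event count would put the 28% in doubt by another route.

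A reader might infer more than the documents support:
- *Minor operations are admitted to the treated side.* They are not, formally. Section 24 defers to Section 6, so this could happen only if staff applied Section 24 alone.
- *The sites differ.* Section 22 says "The research will solely take place at UMMHC Memorial Campus", while Section 13 names no campus for the controls. The control campus is unstated, not shown to be different.
- *The age limits bias the result.* The wording difference touches only men aged exactly 60.
- *The shift can be sized by mixing in the 8.4% rate from Section 13.* That rate covers all thoracic patients, not lower-risk operations in men over 60, and the share of such cases would be a pure assumption. It gives no usable size here.

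**Conclusion.** The point holds in a limited form. The documents do not show that the 28% is the untreated POUR rate of the population Section 6 enrols, the plan's own 2019 rates conflict, and the planned test would not correct a difference in operation type.

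The direction of any bias is unknown. If the controls include non-resections and these carry less risk, as Section 5 suggests, the comparison is tilted against tamsulosin. If the 21% describes the treated population, it is tilted in favour. In that second case the favourable-side error is 12.1% (chi-square) or 9.9% (Fisher), against 2.6% or 2.1%. This is an illustration built on two of the plan's rates, not an estimate of the bias. It assumes that the 21% applies after exclusions and that both rates are true values; neither can be confirmed from the documents.

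This should be corrected before the comparison is made. It concerns bias; a shared definition does not in itself change the sample size or power.

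**What to change.** - Write one definition and use it for both groups in Sections 6, 13 and 24 and in the Table 1 footnote: a list of qualifying operations, inpatient status, one age limit and the campus.
- Repeat the 2019 query with that definition, and state which campus or campuses it covers.
- Reconcile the 21% in Section 5 with the 33.3% in Section 13, giving numerator, denominator and POUR definition for each.
- Restate the 48, the 32, the 28%, the power and the yearly accrual from the new result.
- Add to Section 13 a comparison stratified by, or adjusted for, type of surgery. A shared definition does not remove case-mix differences within major operations, and the variable is already collected.

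The cost is one repeated query and a few edited sentences. The 28% and the accrual figure may change, and with them the power for 60 treated men.
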